## **STATISTICAL ANALYSIS PLAN**

Project Title: Barbershop Talk: HIV Prevention for African American Heterosexual Men

NCT Number: NCT01980771

Date of document: 8/16/18

To describe study sample characteristics across groups at baseline and follow-up and in relation to condomless sex, the  $\chi^2$  test for categorical variables and the independent samples t-test for group differences in continuous variables were utilized. From the original list of measured variables, only those covariates that were associated at  $p < 0.05$  with baseline report of condomless sex or on which there were imbalances between the BTWB intervention and control groups at baseline, were included. Generalized mixed-effects models were used to estimate between-group differences at the participant level, taking into account the hierarchical data structure, with men clustered by barbershop. Differences between the BTWB intervention and control groups in changes in the outcomes were analyzed on an intention-to-treat basis. A binary logistic regression model was used to examine changes in condomless sex, with the six-month value modelled as the outcome and experimental group as the predictor, while controlling for barbershop site of recruitment (random effect), the baseline value of condom use (fixed effect), and covariates (fixed effects). Interaction terms between the covariates and experimental group assignment were tested for statistical significance in a stepwise approach. Data were analyzed using SAS PROC GLIMMIX, version 9.4, 2013.

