Hypothesis 1: Compared to men assigned to an attention control condition, those exposed to the intervention will have lower levels of sexual risk behavior at a 3 and 6 month follow-up.

Hypothesis 2: Compared to men assigned to an attention control condition, those exposed to the intervention will have improved outcomes at 3 and 6 months, on theoretically derived mediators of sexual risk behavior, including interpersonal factors such as attitudes, self-efficacy, communication skills and perceived norms around safer behavior, as well as on factors such as increased individual and community empowerment and decreased HIV-related stigma.

Aim 2: To examine individual and contextual-level factors that explain variation in the efficacy of the intervention.

Hypothesis 3: Intervention impact will be moderated by individual and contextual level-factors such as higher perceived basic needs and housing instability, incarceration and substance use history, higher perceived racism, and traditional gender role norms and attitudes, such that intervention effects will be reduced among men with these risk factors.

Project Rationale:

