The sample size calculation is based on the expected percent of men engaging in high risk behavior after 6 months of follow-up, accounting for the intraclass correlation coefficient (ICC) and estimates of unprotected sex estimated from our pilot dataset of 105 participants from four barbershops. Unprotected sex, defined in this example as two or more sexual partners in the past three months plus at least one episode of unprotected vaginal or anal sex, was reported by 42% of our sample in a previous pilot study of the program. Assuming that 42% of the participants in the control group would engage in high risk behavior, an ICC of 0.03, and a minimum of 23 participants from each barbershop, the study has 80% power to detect an absolute reduction of 12% (relative reduction of 29%) in rates between the two groups with alpha=0.05, two-tailed and 15 barbershops for each intervention group (i.e., 30 clusters and 690 total participants). In order to achieve a sample size of 690 at the six-month follow-up, we estimate that we will need to recruit 875 men in order to account for a loss to follow-up as high as 20%.

Participants:

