All measures included in the program evaluation have been selected based on their demonstrated reliability and validity in published research and in our own previous work in populations similar to the men in this study; we will pilot the instrument prior to administration. To examine hypothesis 1, our main outcome measure will be a composite measure of the proportion of respondents who report two or more partners in the last six months and report unprotected sex during this time. This outcome, which was reported by over 40% of our population in our formative work, is a more informative marker of risk than some other outcome measures used in HIV prevention trials (e.g., any unprotected vaginal or anal sex) in that it helps to differentiate persons engaging in unprotected sex in the context of a single monogamous partnership, versus those who are at higher risk for HIV infection. Other measures of risk will include (1) partner concurrency, (2) number of sexual partners, (3) condom use consistency, and HIV testing. Behaviors will be assessed over the previous three months. Of course, self-report measures of sexual risk behavior are prone to self-report bias as individuals are likely to inflate or deflate their responses based on factors such as gender norms around sexual behavior. However, we will engage in a number of activities to promote honesty in responses by (1) assuring men of the confidentiality of their responses and explain the system that will be used to ensure this, (2) stressing the importance of honest answers to the scientific integrity of the project and for informing community health, (3) and using ACASI. Responses on this measure will be correlated with measures such as sexual behavior and drug use to provide an estimate of the extent to which this bias contributes to scores. Often, clinic-based interventions are able to collect data on more 'hard' outcomes, such as STD rates. The ability to power these studies is based on the fact that participants at baseline typically have and are treated for STD, and that there are known and substantial risks for 'repeat' infections in the control group. In our study, however, it would neither be feasible to conduct STD testing, nor acceptable to do so in the context of a community-based study involving barbershops. As described in our second hypothesis, our intervention is designed to directly influence a set of theoretically derived variables, which in turn are expected to influence sexual risk. These mediating variables include intrapersonal variables such as condom use and HIV testing attitudes, self-efficacy, and subjective norms, as well as perceived skills in communication and negotiation skills around safer sex. These measures are typically ordinal in nature but analyzed as having interval level properties measures

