Statistical analysis will be performed by SAS version 9.2 (SAS Institute, Cary, NC). The primary analysis method for study outcomes to test the main effect of the *Barbershop Talk* intervention will be generalized estimating equations (GEE) models, accounting for the cluster randomization. A logit link function will be specified for binary outcomes (including the primary outcome of engaging in high risk behavior after 6 months of follow-up) while a identity link function will be specified for continuous outcomes. The effects of mediating and moderating variables will be tested by appropriate modeling methods (Jaccard, Turrissi et al. 1990; Shrout and Bolger 2002; MacKinnon, Fairchild et al. 2007). Generalized mixed effects models, treating barbershop as a random effect, will also be fit as sensitivity analyses. All statistical tests will be at the 5% (two-tailed) significance level for main effects and at the 10% (two-tailed) significance level for interactions, with no adjustment for multiple testing.

Timeline:

This is a five year study. We will spend the first six months of the study working with our community advisory board on issues of protocol development, on development and production of high quality graphics for the program, on training of study staff, on securing of IRB approvals for the work and recruiting barbershops. Given our past experience in the barbershops, and our recruitment goal of 875 men, we anticipate that we will enroll participants at the rate of 20-25 per month over a forty-two month period. This would carry our follow-up period through to month six of year five. In the last six months of year five, we will engage in data cleaning and analysis, and dissemination of research findings.

Human subjects considerations:

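### The SAP's only named outcome, condomless sex at six months, is undefined and not tied to the protocol's composite main outcome, whose look-back window is itself stated two ways

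*SAP*

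**What the plan says.** The SAP is a single paragraph. Its one specified model is described as follows: "A binary logistic regression model was used to examine changes in condomless sex, with the six-month value modelled as the outcome". The model adjusts for a baseline value that it calls condom use, and covariates are screened partly on their association with condomless sex at baseline. The SAP refers to outcomes in the plural but lists none, and it does not label any outcome as primary.

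The protocol describes its main outcome in three places:

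- **Program Evaluation:** "our main outcome measure will be a composite measure of the proportion of respondents who report two or more partners in the last six months", combined with unprotected sex over the same period. It adds "This outcome, which was reported by over 40% of our population in our formative work", and says that the composite "is a more informative marker of risk than some other outcome measures used in HIV prevention trials (e.g., any unprotected vaginal or anal sex". After a list of other risk measures, which includes condom use consistency, comes "Behaviors will be assessed over the previous three months".
- **Study design and sample size:** "Unprotected sex, defined in this example as two or more sexual partners in the past three months plus at least one episode"; the episode meant is vaginal or anal sex without protection. The 42% planning rate belongs to this version.
- **Data analysis:** "including the primary outcome of engaging in high risk behavior after 6 months of follow-up".

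Hypothesis 1 states that "those exposed to the intervention will have lower levels of sexual risk behavior at a 3 and 6 month follow-up".

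**The concern.** A reader cannot build the modelled variable from the SAP, and cannot tell whether it is the outcome on which the trial was planned. On its ordinary meaning, condomless sex is close to the type of measure that Program Evaluation ranks as less informative than the composite, because it does not separate a man with one monogamous partner from a man with several. The two measures could give different answers, for example if the program changed the number of partners but not condom use.

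The window matters separately. The same composite with a three-month or a six-month look-back is a different variable at baseline and covers different calendar time at the 3-month visit. Until the components and window are fixed, the result of the SAP's model can be neither reproduced nor set against the planning assumptions.

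**Working it through.** **1. The plan's own figure.** Inputs from Study design and sample size: control rate 42%, 12-point reduction to 30%, ICC 0.03, 23 men per shop, 15 shops per arm, two-sided alpha 0.05, stated power 80%.

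- Men per arm: 15 × 23 = 345.
- Expected events: 345 × 0.42 = 144.9 and 345 × 0.30 = 103.5, a difference of 41.4 men.
- Design effect: 1 + (23 − 1) × 0.03 = 1.66. Effective size: 345 / 1.66 = 207.8 per arm.
- SE under the null: √(2 × 0.36 × 0.64 / 207.8) = 0.0471. SE under the alternative: √((0.42 × 0.58 + 0.30 × 0.70) / 207.8) = 0.0467.
- z = (0.12 − 1.96 × 0.0471) / 0.0467 = 0.59, so power is about 72%.

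The stated 80% is not reproduced. That is a separate matter and nothing below depends on it. What matters here is that these figures are given only for the composite. No rate is given for condomless sex alone, so no corresponding power can be computed.

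**2. Definitions side by side.**

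| Source | Label | Partner component | Window |
|---|---|---|---|
| Study design and sample size | unprotected sex | two or more | three months (attached to partners) |
| Program Evaluation | main outcome, composite | two or more | six months |
| Data analysis | high risk behavior | not restated | not restated |
| SAP | condomless sex; baseline term called condom use | none given | none given |

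Three readings of the SAP fit these rows:

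- It is shorthand for the composite, since the sample size section labels its own composite as unprotected sex.
- It replaces the composite.
- It is a form of the listed condom-use measure, with the composite among the outcomes that the SAP does not name.

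**3. Baseline value under a six-month window.** The entry criteria under Participants require at least two partners, and unprotected sex with a woman, within six months. A six-month composite restates both conditions, so almost every enrolled man should meet it at baseline. The same holds for six-month condomless sex alone. The value need not be exactly 100%, because screening and the baseline interview are separate self-reports. A nearly constant variable gives covariate screening and baseline adjustment little to work with. The SAP does both, which suggests that its variable does not use a six-month window.

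**4. Overlap with the pre-program period.** Program Evaluation counts follow-up from program completion (month 0). At nominal timing:

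- 3-month visit: a six-month look-back covers months −3 to +3, so 3/6 = 50% precedes completion. A three-month look-back covers 0 to +3, so 0%.
- 6-month visit: the spans are 0 to +6 and +3 to +6, so 0% for both.

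**5. Timing of the SAP.** Human subjects considerations keeps identifiable data until January 2022, five years after study end, which implies an end in about January 2017. The SAP is dated 16 August 2018, about 19 months later.

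**The case against.** The strongest reply is that this is incomplete drafting. The SAP never calls condomless sex primary, speaks of several outcomes, and adjusts for condom use, which the protocol lists among its other risk measures. The composite may simply be one of the unnamed outcomes. This stands as a possible reading. A reader might infer that the primary outcome was switched without disclosure, or that Hypothesis 1 was never tested on the main outcome. The documents support neither. The late SAP date does not show a change; it shows only that the documents do not establish when the definition was fixed.

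The window conflict may also be a slip. The sample size section presents its definition as an example, and Program Evaluation says that behaviors are assessed over three months. That sentence follows the other risk measures, however, and may govern only those. The one sentence that names the main outcome says six months, so a choice of three months is not dictated by the text.

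Two further inferences should be resisted. One is to set a near-universal baseline rate against the pilot's 42%, or the figure of over 40%, as a measure of the window effect: the documents do not say that those men met this trial's entry criteria. The other is that the 50% overlap contaminates the primary result. It concerns the 3-month visit only, and the SAP describes no model for that visit.

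What remains is that, on every reading, the variable is undefined in the SAP and the protocol gives its composite two windows.

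**Conclusion.** The point holds as a defect of definition. The SAP does not define the outcome it models or connect it to the composite on which the trial was planned, and the protocol states that composite's partner window as both three and six months.

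Its size cannot be expressed as lost power or bias. What can be stated is that a six-month window would be nearly uninformative at baseline, and that half of it would precede program completion at the 3-month visit. The first rests on screening and baseline reports agreeing closely, the second on nominal visit timing. The six-month primary time point is unaffected by the overlap.

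Confidence is high that the definition is missing and that the windows conflict. It is not high on which of the three readings is true. The matter still needs to be fixed before the result is interpreted, because the variable cannot be reproduced from the SAP on any of them.

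**What to change.** 1. In the SAP, make the composite at six months the primary outcome: at least two partners **and** one or more acts of unprotected vaginal or anal sex, adjusted for its own baseline value.
2. Reconcile Study design and sample size with Program Evaluation to a single window that applies to both components. Three months is supported by the planning definition and because it can vary at baseline. Confirm from the pilot data which window produced the 42%, and from the questionnaire which window was asked.
3. Say what condomless sex means. If it is the composite, use one name throughout, including for the baseline term. If it is a different measure, define it, report it as secondary and disclose the departure from the protocol.
4. State when the definition and window were fixed relative to data access.
5. Optionally, add a six-month-window sensitivity analysis at the 6-month visit, if those items were collected. The documents do not confirm that they were.

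The cost is SAP wording, a short reconciling note for the protocol and one or two extra model runs. The downside is that condomless sex alone, if it is a separate measure, becomes secondary.

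### The SAP's arm-by-covariate interaction tests allow shops to differ in level but not in a covariate's effect, so they reject too often if that effect varies between shops (minor, conditional)

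*SAP*

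**What the plan says.** The SAP is a single paragraph. It describes a logistic model for the six-month outcome with arm as predictor, "controlling for barbershop site of recruitment (random effect), the baseline value of condom use (fixed effect), and covariates (fixed effects"). Barbershop is the only term marked random; baseline condom use and the covariates are marked fixed. The stated purpose of the mixed model is "taking into account the hierarchical data structure, with men clustered by barbershop".

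On moderation it has one sentence: "Interaction terms between the covariates and experimental group assignment were tested for statistical significance in a stepwise approach". The covariates eligible for this are those associated at p < 0.05 with baseline condomless sex, "or on which there were imbalances between the BTWB intervention and control groups at baseline". The software is PROC GLIMMIX. No random slope, empirical (sandwich) variance or degrees-of-freedom method is mentioned.

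The protocol (Data analysis) makes GEE the primary method for main effects and the mixed model a sensitivity analysis. It leaves moderators to unspecified suitable methods and tests "at the 10% (two-tailed) significance level for interactions, with no adjustment for multiple testing". Hypothesis 3, under Aim 2, expects the intervention to work less well among men with certain individual and contextual risk factors.

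**The concern.** Arm is a property of the shop. Most candidate moderators in the protocol (housing, incarceration, substance use, perceived racism, gender-role attitudes) are measured on the man. An arm-by-moderator test therefore asks whether the moderator's slope, averaged over 15 intervention shops, differs from its slope averaged over 15 control shops. Two sources of error enter that contrast: sampling error within shops, and real differences in slope between shops of the same arm. A model with only a shop intercept counts the first and sets the second to zero.

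If the second is not zero, p-values are too small and intervals too narrow, and a covariate can be reported as modifying the intervention's effect when it does not. The 10% level with no multiplicity adjustment leaves little margin for this.

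**Working it through.** **Inputs from the documents.** Protocol, Study design and sample size: 15 shops per arm, 23 men per shop (30 × 23 = 690), ICC 0.03, 42% risk in controls and an absolute reduction of 12 points, so 30% under intervention and a mean risk of (0.42 + 0.30)/2 = 0.36. Protocol, Data analysis: 10% two-sided level for interactions. The plan states no error rate or power for the interaction tests, so there is no figure of its own to reproduce.

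**Assumptions.** The moderator is binary and present in 50% of men. The between-shop SD of its log-odds effect (slope SD) is not in the documents, so a range is used. As a benchmark, the simulations represent ICC 0.03 by a shop-intercept SD of about 0.33.

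**Analytic check.**
- Variance of one shop's estimated slope from sampling alone: 4/(23 × 0.36 × 0.64) = 0.755.
- Adding slope variance s² inflates the interaction's true variance by 1 + s²/0.755, while the model's standard error stays as it was.
- Actual size = 2 × [1 − Φ(z/√inflation)], with z = 1.645 at 10% and 1.960 at 5%.

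| Slope SD | Inflation | Size at nominal 10% | Size at nominal 5% |
|---|---|---|---|
| 0 | 1.00 | 10.0% | 5.0% |
| 0.3 | 1.12 | 12.0% | 6.4% |
| 0.33 | 1.14 | 12.4% | 6.7% |
| 0.5 | 1.33 | 15.4% | 8.9% |
| 0.7 | 1.65 | 20.0% | 12.7% |

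**Simulation, random intercept only, true interaction zero, nominal 10%.**
- Likelihood-ratio test with quadrature, 5,000 trials per setting: 9.8%, 12.0%, 15.5% and 19.8% at slope SD 0, 0.3, 0.5 and 0.7. At nominal 5%: 5.2%, 6.2%, 8.6% and 12.1%.
- Pseudo-likelihood fit, 2,500 trials: 10.1%, 11.4%, 14.8% and 19.4% at SD 0, 0.3, 0.5 and 0.75. With a moderator in 30% of men: 11.0%, 11.3%, 14.5% and 17.3%.
- Two further runs gave the same pattern: about 8% and 10.5% at SD 0, 11–15% at SD 0.3 to 0.33, and 16–20% at SD 0.5 to 0.7.

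**Simulation of the remedies.**
- Random-intercept model with a bias-corrected shop-level sandwich and t on 30 − 2 = 28 df, 1,000 trials: 10.6%, 10.3%, 12.4% and 10.2% at SD 0, 0.3, 0.5 and 0.7 (5.6%, 4.2%, 6.4% and 4.8% at nominal 5%). The Monte Carlo standard error is √(0.1 × 0.9/1,000), about 1 point. A further run that included unequal shops and a 20%-prevalence moderator gave 7–11% and 3–6%. When slopes do not vary, the standard error was only 2–3% wider.
- GEE with a bias-reduced sandwich and t(28), 1,200 trials: about 8–11% and 4–6%.
- Random slope added, t(28), slope SD 0 to 1.0: 8–11% and 3.4–5.4%.

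**The case against.** The best case against is that the size rests on a quantity neither document supplies. With no slope variation the planned test holds its level, and at a slope SD of 0.3 or below the excess is only 1 to 2 points. The only documented clustering is the ICC of 0.03. Slope SDs of 0.5 and 0.7 are variances of 0.25 and 0.49 against about 0.11 (0.33²) for the intercept, so the moderator's effect would have to vary two to four times as much between shops as risk does. The documents neither support nor exclude that. This stands. The intercept-matched figure, about 12%, is the fairest single benchmark, and a claim that any variation at all matters materially would be too strong.

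Second, this is the smaller part of the false-positive risk. Six independent interactions tested at 10% already give 1 − 0.9⁶ = 47% for at least one false positive; at 12.4% each it is 1 − 0.876⁶ = 55%. Stepwise testing adds to that. This also stands: correcting the variance leaves the 47% as it is.

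Third, a reader might infer that Aim 2 and Hypothesis 3 rest on these tests. The SAP does not say so. It never names Hypothesis 3, it screens covariates on baseline association or imbalance, so some Hypothesis 3 moderators may never be tested, and it states no level for interactions; the 10% comes from the protocol. What can be said is that no other moderation test is described.

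A doubt whether the remedy works outside equal-sized shops and a 50% moderator does not stand, given the results with unequal shops and a 20% moderator.

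**Conclusion.** The concern holds as a conditional and minor one. Reading the SAP's barbershop random effect as an intercept only is an inference, but the plain one, since every covariate is labelled fixed. On that reading the interaction tests for man-level covariates assume an identical covariate effect in every shop of an arm, and nothing in either document justifies this. At an assumed slope SD of 0, 0.33, 0.5 and 0.7 the nominal 10% test runs at about 10%, 12%, 15% and 20% (30 shops × 23 men, moderator in half the men).

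It does not apply to a purely shop-level moderator, for which the shop intercept already carries the relevant variation. Nor does it extend to the main arm comparison. A reader might also infer that false moderators have been declared; without an estimate of slope variation the documents do not show that.

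**What to change.** Add one sentence to the SAP: the random-intercept model is kept, but each arm-by-covariate test and interval for a man-level covariate uses a small-sample-corrected, shop-level robust variance with about 28 between-shop degrees of freedom. In PROC GLIMMIX this is a bias-corrected EMPIRICAL option. The protocol's GEE with a corrected sandwich would serve equally well. A random slope for the tested covariate can be fitted as a check where it converges.

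The SAP is dated 8/16/18 and written in the past tense. If the analysis is already done, re-run the interaction tests this way, label them as a re-analysis and report both sets of results.

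The cost is one procedure option, slightly wider intervals and a mildly conservative test. The change does not deal with stepwise selection or the absence of multiplicity adjustment, which need their own treatment.
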